# **Learning of Motor Control Exercises with Different Methods and its Effects on Treatment Outcomes in Patients with Chronic Non-specific Low Back Pain: A Randomised Controlled Trial**

## **Introduction**

### **Item 2a. Scientific background and explanation of rationale.**

Non-specific low back pain is defined as low back pain not attributable to a recognizable, known specific pathology (1). According to The Turkish Statistical Institute, it is the most common health problem in The Turkish Population (2).

For this common problem, European Guidelines for the Management of Chronic Nonspecific Low Back Pain defined exercise as first line treatment (3). There are various exercise approaches for the treatment. Treatment effect sizes of these approaches are generally same, motor control exercises better than general exercises (4,5).

For see the full effect of exercise treatment, exercise adherence should be high. In patients with chronic non-specific low back pain, the complex nature of the core-stabilization exercises decreases the exercise adherence (6,7). Some novel studies show that multimedia learning can increase efficiency of complex skill learning and can be better from classic face to face learning (8,9). Therefore, we designed this study to determine the effect of multimedia learning on the effectiveness of motor control exercise therapy.

### **Item 2b. Specific objectives or hypotheses**

In this study, we planned to determine if multimedia learning is better than standard face-to-face learning for core stabilization exercises.

## **Methods**

### **Item 3a. Description of trial design (such as parallel, factorial) including allocation ratio**

This will be a block randomized (Block number was 10.), allocation ratio 1:1, assessor blinded, controlled, parallel-group study conducted in the Hacettepe University, Turkey.

## **Item 4a. Eligibility criteria for participants.**

Inclusion Criteria:

- Chronic (>3 month), non-specific low back pain
- 25- 55 years old
- Have a capacity can understand exercise instructions (Montreal Cognitive Assessment > 21)
- Being a computer-literate

Exclusion Criteria:

- Root nerve signs
- Cauda equina syndrome
- Fracture in the vertebra
- Tumor
- Have a neurologic disease
- History of spine surgery
- Knowing motor control exercises
- Visual impairment
- Hearing loss

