## **Item 5. The interventions for each group with sufficient details to allow replication, including how and when they were actually administered.**

Conventional treatment will be applied to both groups. Conventional treatment includes application of superficial temperature, soft tissue relaxation techniques and joint mobilizations. Only difference between groups will be exercise teaching methods. Each patient will receive an equal session routine physiotherapy treatment and the treatment will take an average of 60 minutes. On the other hand, individualization of the program will be done according to the criteria of transition to upper exercise, and it will be recorded when each patient has a higher exercise.

The exercise program will be performed according to the protocol of Hicks et al. And no medical device will be used.

The exercise program which will be use in the study for both groups (10,11):

First Session:

- Patient will be watch a pain physiology multimedia video prepared by study team. If patient have a question after watching the video, will be encouraged to ask her physiotherapist.
- The anatomy and kinesiology of the trunk stabilization, and motor control exercise principles will be explained to patient. For this purpose, face-to-face group receive information from physiotherapist with help of pictures while multimedia learning group watch a video with animations and narrations prepared by study team and reviewed by a specialist team.

2-16. seasons:

- Exercises Program
  - Transversus abdominus (30 repetitions with 8-s hold)
    - Abdominal Draw-in Maneuver (30 repetitions with 8-s hold)
    - Abdominal Draw-in Maneuver + heel slides (30 repetitions with 8-s hold)
    - Abdominal Draw-in Maneuver + leg lifts (20 repetitions with 8-s hold)
    - Abdominal Draw-in Maneuver + bridging (20 repetitions with 8-s hold, then progress to 1 leg)
    - Abdominal Draw-in Maneuver + standing (30 repetitions with 8-s hold)
    - Abdominal Draw-in Maneuver + standing row exercise (20 repetitions per side with 6-s hold)
    - Abdominal Draw-in Maneuver + walking (30 repetitions with 8-s hold)
  - Paraspinals/multifidi
    - Abdominal Draw-in Maneuver + Quadruped arm lifts (30 repetitions with 8-s hold)
    - Abdominal Draw-in Maneuver + Quadruped leg lifts (30 repetitions with 8-s hold)
    - Abdominal Draw-in Maneuver + Quadruped alternate arm and leg lifts (30 repetitions with 8-s hold)
  - M. Quadratus lumborum and m. obliquus abdominis

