## **Item 6a. Completely defined pre-specified primary and secondary outcome measures, including how and when they were assessed**

### **Evaluation of the severity of pain:**

Visual Analog Scale will be used before the treatment, at before and after every treatment session and at the third month after the treatment. This scale is a 100 millimeter line drawn horizontally on an A4 sheet of paper. The left end of the line shows “no pain at all”, the right end shows “my pain is as bad as it could be”, while the remaining part shows the intermediate values. The patient is asked to mark the severity of the pain on the chart. Validity and reliability were made. The minimal clinical significance difference in chronic low back pain was 20 millimeters.

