## **Item 7a. How sample size was determined**

For the calculation, version 2.9.1.2 of the G \* Power software was used (14). The preliminary (a priori) power calculation protocol, the effect size for the pain variable, was calculated as 1.23 based on a study by Amit et al (15). Type I error probability was 0.05 and power was accepted as 0.80. The distribution rate of groups 1 is assumed. As a result, the number of people to be taken for each group is calculated as 12. Assuming that the loss of patients during the treatment will be 10%, it is expected to complete the study with 30 patients in total.

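### No minimum pain intensity at entry: patients near the bottom of the pain scale can be randomised and can only shrink the pain contrast, by an amount the documents do not let anyone fix

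*Combined protocol and SAP*

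**What the plan says.** Item 4a is the only statement of eligibility. Its pain criterion is "Chronic (>3 month), non-specific low back pain", which covers duration and type. The other inclusion criteria concern age, cognition and computer literacy. No exclusion concerns pain level, and no other section sets a minimum VAS or disability score.

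Item 6a describes the pain measure: "This scale is a 100 millimeter line drawn horizontally on an A4 sheet of paper". Its left end means no pain, so the score cannot fall below 0. The same paragraph says "The minimal clinical significance difference in chronic low back pain was 20 millimeters". Pain is recorded before treatment, around each session and at three months.

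Item 5 says "Conventional treatment will be applied to both groups" and "Only difference between groups will be exercise teaching methods". The control arm therefore receives heat, manual techniques and the full exercise programme.

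Item 7a sizes the trial on pain: "the effect size for the pain variable, was calculated as 1.23". It arrives at 12 per group and plans 30 in total. Item 12a plans an ANOVA with a group interaction and mentions no adjustment for baseline pain.

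**The concern.** Someone who enters at 15 mm qualifies but cannot improve by 20 mm. Because controls are also treated, the room needed is larger than 20 mm. If controls improve by c mm, a multimedia patient needs at least c + 20 mm at entry to show 20 mm more. Below that level the scale cuts off part of any true benefit, and a patient who enters well below c shows almost none of it on pain.

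At stake is how a null pain result would be read. With about 15 patients per arm and no entry threshold, a small observed difference could mean that the teaching method adds nothing, or that many patients had too little pain to show it. The plan offers no way to tell these apart.

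**Working it through.** **1. The plan's own figure.** Inputs from Item 7a: d = 1.23, "Type I error probability was 0.05 and power was accepted as 0.80", equal allocation. A two-sided two-sample t-test (noncentral t) needs 11.42, so 12 per group, with power 0.82. The stated 12 reproduces. Allowing for 10% loss, 24/0.90 = 26.7, so 27. The planned 30 is above that and gives 15 per arm, where power at d = 1.23 is 0.90.

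**2. Link to 20 mm.** Item 7a gives no SD and no difference in mm. An effect size of 1.23 equals 20 mm only if SD = 20/1.23 = 16.3 mm.

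**3. Room on the scale.** The entry pain needed to show 20 mm beyond control is c + 20. For assumed c of 10, 20 and 30 mm this is 30, 40 and 50 mm.

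**4. Effect on the contrast and on power.** Assumptions, none from the documents: entry VAS normal with SD 20 mm limited to 0-100, residual SD 12 mm, true extra benefit 20 mm. Follow-up = entry − c − (20 in the multimedia arm) + noise, cut at 0 and 100. The outcome analysed is change from entry, which is what a group-by-time interaction tests. Power uses d = mean contrast / SD of change, so it includes the effect of the floor on the spread as well as on the mean.

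No minimum at entry; each cell gives contrast in mm / power at 15 per arm:

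| Control improvement | Mean entry 30 | 40 | 50 | 60 |
|---|---|---|---|---|
| 10 mm | 14.1 / 0.92 | 16.2 / 0.96 | 18.0 / 0.98 | 19.0 / 0.99 |
| 20 mm | 10.7 / 0.67 | 13.5 / 0.86 | 16.0 / 0.95 | 17.9 / 0.98 |
| 30 mm | 7.3 / 0.32 | 10.3 / 0.56 | 13.3 / 0.82 | 16.0 / 0.94 |

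At 12 per arm, the 20 mm row has power of about 0.57, 0.76, 0.89 and 0.95.

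**5. What a minimum does and costs.** The share below a cut k is [Φ((k−μ)/20) − Φ(−μ/20)] / [Φ((100−μ)/20) − Φ(−μ/20)].

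- k = 30, μ = 40: (0.3085 − 0.0228)/(0.9987 − 0.0228) = 29%. At μ = 30 it is 46%, and at μ = 60 it is 7%.
- k = 40: 49% at μ = 40 and 67% at μ = 30.

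With control improvement 20 mm and μ = 40, a 30 mm minimum raises the contrast from 13.5 to 17.1 mm, and a 40 mm minimum raises it to 18.7 mm.

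Now suppose excluded patients are not replaced, so 15 per arm shrinks by the share screened out. With a 30 mm minimum and control improvement 20 mm, power still goes from 0.86 to 0.93 at μ = 40 and from 0.67 to 0.83 at μ = 30. The minimum loses a little where controls improve only about 10 mm and entry pain is low. At μ = 30 it leaves 15 × 0.54 = 8.1 per arm with d = 18.7/11.2 = 1.67, and power goes from 0.92 to 0.87.

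**The case against.** The strongest reply is that the harm is conditional and the open criterion is a legitimate choice of a broad population.

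- **Size.** Every mm figure rests on assumed baseline pain. Recruits come from a back and neck clinic, and nothing shows that many would enter near the floor. Nothing rules it out either. This stands: the documents fix the direction of the loss but not its size.
- **A false null from a few patients.** A reader might infer that a handful of low-pain entrants would by themselves produce a false finding of no difference. The documents do not support that. The floor narrows the spread of change scores as well as the mean. With mean entry pain 40 mm and control improvement 20 mm, 49% of patients start below 40 mm, yet power is 0.86 at 15 per arm, above the planned 0.80 (though about 0.76 at 12). A simpler dilution calculation that holds the SD fixed (20% of patients with no room, d = 1.23 × 0.8 = 0.98, power 0.74 at 15 per arm) overstates the loss for a change-score analysis.
- **Uninformative patients.** A reader might also infer that low-pain patients say almost nothing about the trial's question. Adherence, progress rate and walking are not limited by the VAS floor, and Item 6a does not name pain as primary. Even on pain, patients between 20 and 40 mm contribute a partial contrast when controls improve by 20 mm.
- **A 40 mm minimum.** It may seem to follow from the protocol's figures, but half of it is an assumed control improvement, and Item 6a does not present 20 mm as the target between-arm difference. It could also cost half or more of the candidates.
- **Adjusting instead.** In the same model, adjusting for baseline VAS gives power of 0.93 at mean 40 and 0.85 at mean 30 with nobody excluded. That is a real gain, but the contrast in mm stays compressed.

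**Conclusion.** The point holds in a limited form. Eligibility has no pain-intensity threshold, although the trial is sized on a pain scale bounded at 0 and compares two actively treated arms. Entrants near the floor can only reduce a true pain benefit.

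Under the stated assumptions with control improvement of 20 mm, a true 20 mm benefit appears as about 11 to 18 mm across mean entry pain of 30 to 60 mm. The loss is serious if typical entry pain is about 30 mm, or if controls improve by about 30 mm from a mean of 40 mm or less. It is small at a mean of 60 mm with control improvement of 20 mm or less. The documents do not say which case applies.

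This is not evidence that the sample size calculation is wrong: its 12 per group reproduces. Nor does it show that the trial will miss its planned power. It is a gap that a modest eligibility line would narrow.

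**What to change.** Add to Item 4a a minimum pre-treatment VAS, with its rationale. It should be no lower than the protocol's own 20 mm important difference; 30 mm is a reasonable example. Use 40 mm only if screening data show that recruitment allows it. Take the reading before the allocation envelope is opened. State that the pain conclusion applies to patients at or above the chosen level. If the investigators prefer no minimum, they should justify that and adjust the pain analysis for baseline VAS, accepting that this does not remove the floor.

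**Cost.** No new measurement is needed, because the VAS before treatment is already planned. The price is recruitment and generality. In the assumed scenarios a 30 mm minimum turns away about 7% to 46% of candidates (29% at a mean of 40 mm), at a single centre with data collection planned from June to September 2019. Selecting on the baseline reading also adds some regression to the mean to the change within each arm. This affects both arms alike and does not bias the comparison between them.

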## **Item 4b. Settings and locations where the data were collected**

This study will carry out at the Back and Neck Health Unit at Hacettepe University Faculty of Physiotherapy, Ankara, Turkey. Anticipated data collection date between June 2019 and September 2019.

## **Item 5. The interventions for each group with sufficient details to allow replication, including how and when they were actually administered.**

Conventional treatment will be applied to both groups. Conventional treatment includes application of superficial temperature, soft tissue relaxation techniques and joint mobilizations. Only difference between groups will be exercise teaching methods. Each patient will receive an equal session routine physiotherapy treatment and the treatment will take an average of 60 minutes. On the other hand, individualization of the program will be done according to the criteria of transition to upper exercise, and it will be recorded when each patient has a higher exercise.

The exercise program will be performed according to the protocol of Hicks et al. And no medical device will be used.

The exercise program which will be use in the study for both groups (10,11):

First Session:

- Patient will be watch a pain physiology multimedia video prepared by study team. If patient have a question after watching the video, will be encouraged to ask her physiotherapist.
- The anatomy and kinesiology of the trunk stabilization, and motor control exercise principles will be explained to patient. For this purpose, face-to-face group receive information from physiotherapist with help of pictures while multimedia learning group watch a video with animations and narrations prepared by study team and reviewed by a specialist team.

2-16. seasons:

- Exercises Program
  - Transversus abdominus (30 repetitions with 8-s hold)
    - Abdominal Draw-in Maneuver (30 repetitions with 8-s hold)
    - Abdominal Draw-in Maneuver + heel slides (30 repetitions with 8-s hold)
    - Abdominal Draw-in Maneuver + leg lifts (20 repetitions with 8-s hold)
    - Abdominal Draw-in Maneuver + bridging (20 repetitions with 8-s hold, then progress to 1 leg)
    - Abdominal Draw-in Maneuver + standing (30 repetitions with 8-s hold)
    - Abdominal Draw-in Maneuver + standing row exercise (20 repetitions per side with 6-s hold)
    - Abdominal Draw-in Maneuver + walking (30 repetitions with 8-s hold)
  - Paraspinals/multifidi
    - Abdominal Draw-in Maneuver + Quadruped arm lifts (30 repetitions with 8-s hold)
    - Abdominal Draw-in Maneuver + Quadruped leg lifts (30 repetitions with 8-s hold)
    - Abdominal Draw-in Maneuver + Quadruped alternate arm and leg lifts (30 repetitions with 8-s hold)
  - M. Quadratus lumborum and m. obliquus abdominis
    - Side support with knees flexed (30 repetitions with 8-s hold)
    - Side support with knees extended (30 repetitions with 8-s hold)
- Home exercise program: The patient will be asked to perform the given exercise 20 minutes a day.

- Multimedia exercise videos will be included 2D animations with compatible narrations. These videos were prepared based on cognitive theory of multimedia learning, and tested with Learning Object Review Instrument version 2.0 by a board of ten years experienced physiotherapy experts.

## **Item 6a. Completely defined pre-specified primary and secondary outcome measures, including how and when they were assessed**

### **Evaluation of the severity of pain:**

Visual Analog Scale will be used before the treatment, at before and after every treatment session and at the third month after the treatment. This scale is a 100 millimeter line drawn horizontally on an A4 sheet of paper. The left end of the line shows “no pain at all”, the right end shows “my pain is as bad as it could be”, while the remaining part shows the intermediate values. The patient is asked to mark the severity of the pain on the chart. Validity and reliability were made. The minimal clinical significance difference in chronic low back pain was 20 millimeters.

### **Evaluation of Disability**

Disability will be evaluated by Oswestry Disability Scale 2.0 Turkish version. This version contains 10 multiple-choice questions that question how low back pain affects a person in his or her daily life. Each question has 6 options. As the disability increases, the score of each problem increases. In the worst case you can get 50 points. The last point is the patient's score 100.

### **Evaluation of Walking-Distance and Spatiotemporal Variables of Walking**

The 6-minute walk test, which measures how far the patient can walk in 6 minutes, will be used to measure functional durability. The time-distance variables of the walk will be evaluated by Optogait (Microgait Company, Bolzano, Italy). The hiking band and the Optogait device are clinical devices. The OptoGait system includes 10 data retention bars positioned parallel to each other between 1.20 m (10m x 1.20m). On each rod, 96 LED diodes are placed at a height of 3 mm from the ground, 1 cm apart. According to the design of the device, when the patient passes between two bars positioned parallel to the floor, the device detects the communication interruptions between the bars caused by his

feet. Calculates the duration and location. In addition, timing, size and distance are detected, time-distance characteristics are automatically calculated (12,13). OptoGait not only identifies numerical data, but also enables it to perfectly synchronize with the events that detect the images of the tests performed via small cameras that can be positioned freely (13).

## **Evaluation of Progress Rate**

A transition date to the upper exercise will be recorded. The duration of the entire program will be calculated in days.

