## **Item 11a. If done, who was blinded after assignment to interventions (for example, participants, care providers, those assessing outcomes) and how**

The patient's group will not be written on the evaluation paper, so they will be kept from researcher [name].

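### Progress rate rests on transition decisions made during treatment sessions that cannot be delivered blind, so the unqualified assessor-blinded label is not supported for this outcome

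*Combined protocol and SAP*

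**What the plan says.** The section Evaluation of Progress Rate, under Item 6a, defines the outcome in two sentences. The first is "A transition date to the upper exercise will be recorded"; the second adds the length of the whole programme, counted in days. The section names no judge, no recorder and no blinding.

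Item 5 describes where the transition comes from: "individualization of the program will be done according to the criteria of transition to upper exercise". The criteria are mentioned but not listed. Item 5 gives repetitions and hold times for each exercise and cites a published exercise protocol, but does not say that reaching those figures triggers a move up. On recording, Item 5 says only that "it will be recorded when each patient has a higher exercise".

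On the contrast between arms, Item 5 says "Only difference between groups will be exercise teaching methods". For the explanatory first session it says "face-to-face group receive information from physiotherapist with help of pictures while multimedia learning group watch a video with animations and narrations".

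On blinding, Item 3a describes the trial as "allocation ratio 1:1, assessor blinded, controlled, parallel-group study", with no limit to particular outcomes. Item 11a gives the only method: the patient's "group will not be written on the evaluation paper", so that one researcher does not learn it.

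**The concern.** Item 2b asks whether multimedia learning is better than face-to-face learning for these exercises, and progress rate is arguably the listed outcome nearest to learning itself. If the person who decides on a move up knows the arm, an expectation about either method can enter the date. The result could then differ between arms with no difference in learning, and no later analysis could separate that from a real effect. The same decision sets the exercise level at which the patient trains, so it may also affect the treatment received. A reader who sees the assessor-blinded label would assume that progress rate is protected in the same way as the other outcomes.

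**Working it through.** The plan states no figure for progress rate. Its only calculated figure, 12 per group in Item 7a, concerns pain, and this point does not depend on it. The check is mainly a comparison of sections.

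1. **Where the outcome arises.** Item 5 ties the move up, and its recording, to the individualised exercise programme of sessions 2 to 16. The transition is therefore an event within treatment, not a measurement taken at a separate assessment visit.

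2. **How often a judgement is made.** Item 5 lists 7 transversus, 3 paraspinal and 2 side-support exercises. If each list is an ordered ladder, the moves are (7 − 1) + (3 − 1) + (2 − 1) = 9, or 10 with the one-leg step within bridging. The section on progress rate does not say which of these is the date analysed, or whether programme duration in days follows from them.

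3. **Who can be blind at that moment.** Teaching method is the only planned difference, and in the face-to-face arm a physiotherapist gives the teaching. Whoever teaches that arm must know it. No section says that the blinded researcher attends sessions or rules on progression.

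4. **What Item 11a covers.** It hides the group from a researcher who handles a form. Even if the transition date is later copied to that form, the date records a decision already taken.

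5. **Room for judgement.** Item 5 mentions criteria, so progression is not left wholly to discretion. Because the criteria are not written out, a reader cannot tell how mechanical they are or check that both arms are judged alike.

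6. **Illustration of size, by assumption only.** The documents do not size any shift. Suppose there is no true effect, the outcome is roughly normal, and judgement shifts one arm by δ standard deviations. In a two-sided 5% t-test with n per arm, the chance of a significant result is the power at noncentrality δ√(n/2), on 2n − 2 degrees of freedom. Item 7a's total of 30 at 1:1 gives n = 15 (28 df); its calculated minimum gives n = 12 (22 df).

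| Assumed shift δ (SD) | Noncentrality, n = 15 | Chance of p < 0.05, n = 15 | Chance of p < 0.05, n = 12 |
|---|---|---|---|
| 0.25 | 0.25 × √7.5 = 0.68 | 10% | 9% |
| 0.50 | 0.50 × √7.5 = 1.37 | 26% | 22% |
| 0.75 | 0.75 × √7.5 = 2.05 | 51% | 42% |

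The table shows what would follow if such a shift existed. It is not evidence that one does.

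**The case against.** The strongest reply is that the plan never says the treating therapist sets the dates. Both relevant sentences are passive, the evaluation paper is not defined, and progress rate sits among the evaluations in Item 6a, so the blinded researcher might record it. This stands as far as it goes: a reader might take it as stated fact that an unblinded therapist sets the dates, and the documents support that only as a strong inference. It does not rescue the label, because no described safeguard reaches the decision, whoever writes it down.

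Second, progression follows criteria under a cited protocol. This also stands, and it rules out the reading that transitions are simply the therapist's choice. The criteria are not listed, however, so the plan does not show that judgement is excluded.

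Third, unblinded delivery is unavoidable here, progress rate is not designated primary, and the sample size rests on pain. All true. This limits the importance of the point and does not answer it.

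Fourth, a session log does not cure the problem. The therapist still counts repetitions, an early move ends the log for the lower exercise before the criterion is shown as met, and any effect on the treatment received remains. This is fair, and the fix has to allow for it.

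Finally, a reader might try to express the bias in days. That needs a session pace, a programme length and a number of sessions gained per step. The eight-week adherence assessment is not stated to be the end of the programme, and nothing in the documents sizes the gain, so no figure in days is supported.

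**Conclusion.** The point holds in conditional form. Progress rate depends on transitions judged during sessions that cannot be delivered blind. The set-up strongly suggests that the treating physiotherapist judges them, though the plan does not say so. The one blinding measure does not reach that judgement, so the unqualified assessor-blinded label is not supported for this outcome, and a difference in either direction could reflect arm-dependent judgement.

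The documents do not establish that bias will occur, which way it would run, or how large it would be. The percentages above rest wholly on assumed shifts. The point concerns progress rate alone and should be addressed before data collection, with moderate weight.

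**What to change.** - **Item 6a, criteria.** Write out the transition criteria that Item 5 already refers to, and name who judges and who records each transition. No new criterion is proposed here.
- **Item 6a, log.** Have the therapist log, at each session, the repetitions and hold time achieved on the current exercise.
- **Item 6a, derivation.** Have the researcher already kept blind derive the outcome date from coded logs that do not show the group, as the first session at which the existing criteria were met. Flag patients moved up before the log shows this, and report their number by arm.
- **Items 3a and 11a.** Limit the assessor-blinded claim to outcomes collected by the blinded researcher. Report progress rate as based on unblinded therapist records.

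The cost is one log line per session and a short derivation step by existing staff. Care does not change. The therapist still counts the repetitions, and any effect of early moves on the treatment received remains, so bias in the outcome is reduced and made visible but not removed.
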